# 18 STUDY REPORT AND PUBLICATIONS

A clinical study report will be prepared following completion of the study. An Investigator signatory may be identified for the approval of the report if required by applicable regulatory requirements.

The study data will be owned by Indivior. Publication of any and all data will be at the discretion of Indivior. The Investigator will not disseminate, present or publish any of the study data without the prior written approval from Indivior to do so.

# 19 STUDY DISCONTINUATION

Both Indivior and the Investigator reserve the right to terminate the study at the Investigator's site at any time. Should this be necessary, Indivior, or a specified designee will inform the appropriate Regulatory Authorities of the termination of the study and the reasons for its termination, and the Investigator will inform the IRB of the same. In terminating the study, Indivior and the Investigator will assure that adequate consideration is given to the protection of the subjects' interests.

# **20 CONFIDENTIALITY**

All subject-identifying documentation generated in this study is confidential and may not be disclosed to any persons not directly concerned with the study without written permission from the subject. However, authorized regulatory officials and Indivior personnel (or their representatives) will be allowed full access to inspect and copy the records. All subject bodily fluids and/or other materials collected shall be used solely in accordance with this protocol and the ICF signed by the subject, unless otherwise agreed to in writing by Indivior.

Each subject will be identified assigned subject number when reporting study information to any entity outside of the study centre. Data containing subject identification will not be removed from the clinic without first redacting subject identifiers.

Cytochrome P450 3A4 Inhibitors						
Name	Example Brand Name(s)	Name	Example Brand Name(s)			
Itraconazole	Sporanox					

Cytochrome P450 3A4 Inducers					
Name	Example Brand Name(s)	Name	Example Brand Name(s)		
Barbiturates	Nembutal, Luminal	Phenytoin	Dilantin, Phenytek		
Carbamazepine	Carbatrol, TEGretol	Pioglitazone	Actos		
Dexamethasone	Decadron	Primidone	Mysoline		
Efavirenz	Sustiva, Atripla	Rifabutin	Mycobutin		
Ethosuximide	Zarontin	Rifampin	Rifadin, Rimactane		
Glucocorticoids	Prednisone, Medrol, Millipred	Hypericum perforatum	Medicinal herb		
Glutethimide	Elrodorm, Noxyron.	Sulfinpyrazone	Anturane		
Modafinil	Provigil				
Nevirapine	Viramune				
Oxcarbazepine	Trileptal, Oxtellar XR				
Phenobarbital	Luminal				

Source: http://medicine.iupui.edu/clinpharm/ddis/clinical-table/

1 INTRODUCTION

This statistical analysis plan (SAP) provides the detailed methodology for summary, pharmacokinetic and statistical analyses of the data collected in Study INDV-6000-404.

This SAP supersedes the statistical considerations identified in the protocol; where considerations are substantially different, they will be so identified in Section 6.2. Any deviations from the analyses described below, as well as Post-hoc analyses, will be documented in the clinical study report (CSR).

Specification of tables, listings and figures (TLFs) are provided in a separate document.

1.1 Version History

Table 1	Table 1 SAP Version History Summary						
SAP Version	SAP Approval Date	Associated Protocol	Protocol Amendment Approval Date	Change	Rationale		
1.0	08 Apr 2020	Amendment 1	04Dec2019	Not Applicable	Original version		
2.0	02 Jul 2020	Amendment 1	04Dec2019	In Section 4 added that all subjects screened received SUBLOCADE, so a screened population was not defined Section 5.1.4.5, definition of treatment completion was removed.	Clarification. Not needed for analysis.		
				In Section 5.1.5, removed the statement regarding concomitant medication summary tables being produced	Concomitant medications are only being listed, not summarized, so this statement was not applicable.		

only if there are >6 medications.	
In Section 5.4.2, removed information about derived variables.	The prior and concomitant medication data is only being listed and not summarized, so derived variables are not necessary.
In Section 5.5.1, removed adverse events of special interest from the adverse event overall summary table.	A flag for adverse events of special interest was not derived since there were no adverse events reported in the study.
In Section 5.5.5, correct the description of the IV opioid use analysis.	Data is from study 403 screening, not each visit.
In Section 6.2, removed 'the reporting of concomitant medications as a listing only and no summary table in the case of ≤ 6 medications' as a change from the	The protocol states prior and concomitant medications will only be listed, so there was no change to the protocol planned analysis regardless of number of medications reported.

	protocol plann analysis.	ed
	Removed Sect regarding parti prior/concomit medication sta dates and assig prior and conc medication fla	medication data is only being listed and not summarized, so derived variables are not necessary.
	In Section 6.7, variables not b summarized	

1.2 Objectives and Endpoints

Table 2 Objectives and Endpoints	
Objectives	Endpoints
Primary	
The objective of this study is to assess the longer-term safety of an abbreviated initiation protocol of SUBLOCADE in subjects who have completed INDV-6000-403. It is also to provide treatment to these individuals while they seek longer-term care arrangements, as it (on average) takes an individual with OUD 6 months between seeking treatment and achieving an appointment at a provider within the US.	The proportion of subjects with treatment emergent adverse events (TEAEs) at any time during the treatment period.
Other Safety Endpoints	
	Assessment of study medication-related TEAEs, serious TEAEs, study medication-related serious TEAEs, TEAEs leading to treatment discontinuation and concomitant medications.

1.3 Study Design

Only subjects who have completed the End of Treatment (EOT) procedures for Study INDV-6000-403, have signed the INDV-6000-404 informed consent form (ICF), and meet all the enrolment criteria may be considered for inclusion in this study.

The INDV-6000-403 EOT visit is 28 days after the subject's first dose of SUBLOCADE in INDV-6000-403, therefore the INDV-6000-403 EOT and the INDV-6000-404 screening and Day 1 visit for this study will occur within 2 days, thus the INDV-6000-403 EOT assessments will serve as the screening assessments for the Screening Visit (Day 1) of this study.

Any AEs and concomitant medications ongoing at the INDV-6000-403 EOT will be rerecorded for this study. In addition, demographics, height, medical/psychiatric, substance and drug of abuse history will not be re-collected and will be taken from the INDV-6000-403 screening assessments. As per protocol amendment 1, a detailed detox and MOUD (medication for opioid use disorder) treatment history will be collected at screening. For those subjects who have enrolled in the study prior to approval of protocol amendment 1, their detox and MOUD treatment history will be collected retrospectively at their next visit.

On Day 1, eligible subjects will receive a subcutaneous injection of 300mg SUBLOCADE. Before departing the site, any new adverse events (AEs) or concomitant medications will be recorded.

Subjects will return to the site for monthly injection visits every 4 weeks (-2 / +7 days) for a total of up to 5 injections. At Injection Visits 2 through 5, subjects will be evaluated in accordance with local standard of care and results for the following procedures will be recorded: urine pregnancy test (to be performed before SUBLOCADE administration for all female subjects who are of childbearing potential); urine drug screen (UDS) and evaluation of previous injection site for potential reaction and evidence of attempts to remove the depot. For injections 2 to 5, subjects may receive either a dose of 100 mg SUBLOCADE or 300 mg SUBLOCADE, based on the medical judgment of the Investigator, per the SUBLOCADE United States Prescribing Information (USPI). During each visit the subject will be assessed for AEs and use of concomitant medications.

All subjects will receive counselling as determined by local standard of care throughout the study from Day 1 through EOT.

All subjects who receive SUBLOCADE (including those who wish to discontinue early), will be encouraged to attend the EOT/ET visit 4 weeks after SUBLOCADE administration.

At the EOT/ET Visit, results for the following procedures and assessments will be recorded: urine pregnancy test for all female subjects who are of childbearing potential; evaluation of previous injection site for potential reaction and evidence of attempts to remove the depot; UDS; use of concomitant medications and assessment for AEs. At every visit, options for continued care should be discussed with the subject.

Any subject with ongoing AEs or concomitant medications at the EOT Visit will also be followed up by telephone 4 weeks later for a safety follow up to assess the ongoing AEs or concomitant medications only.

Table 3 Schedule of Assessments – Overview of Study

Procedure/Assessment	Screening	Injection 1	Injection 2	Injection 3	Injection 4	Injection 5	ET / EOT ⁹	Safety Follow up ¹⁰
Visit Number		1	2	3	4	5	6	7
Day(s)		1	29	5 7	85	113	141	169
Window (days)		+2	-2 / +7	-2 / +7	-2 / +7	-2 / +7	-2 / +7	-7 / +7
Informed Consent ¹	X							
Inclusion/Exclusion Criteria	X							
Demographics ²	403 ²							
Medical/Psychiatric History ²	403 ²							
Substance/Drug Use History ²	403 ²							
Height ²	403 ²							
Weight/BMI ³	403 EOT ³							
Urine Pregnancy Test ⁵	403 EOT ³		X	X	X	X	X	
UDS ⁶	403 EOT ³		X	X	X	X	X	
Injection Site Evaluation ⁷	403 EOT ³		X	X	Х	Х	X	
AE Assessment	X ⁴		X	X	X	X	X	
Concomitant Medications	X ⁴		X	X	Х	X	X	X
Study Drug Administration		X	X	X	X	X		
MOUD and treatment History ¹¹	X							
Counselling ⁸				X	•	•		

AE=adverse event; BMI=body mass index; EOT=End-of-Treatment; ET=Early Termination; OUD=opioid use disorder; UDS=urine drug screen; MOUD=medication for opioid use disorder

- 1. Written informed consent must be obtained after completion of all INDV-6000-403 EOT procedures and before any INDV-6000-404 study-specific assessments/procedures are initiated.
- 2. This data will not be re-collected; the data from the INDV-6000-403 screening visit will be used.
- 3. This data will not be re-collected; the data from the INDV-6000-403 EOT visit will be used.
- 4. Any ongoing (at the INDV-6000-403 EOT) or new AEs or concomitant medications in this study will be recorded.
- 5. Required for female subjects of childbearing potential only, to be performed before SUBLOCADE dosing at Visits 1 to 6.
- 6. Qualitative test to be performed before SUBLOCADE dosing at Visits 1 to 6.
- 7. Injection site will be evaluated for signs of attempted removal before SUBLOCADE dosing at Visits 1 to 6. Any injection site reactions or infections will be recorded as AEs.
- 8. All subjects will receive counselling as determined by local standard of care throughout the study from Day 1 through EOT.
- 9. All subjects who receive SUBLOCADE (including those who wish to discontinue early), will be encouraged to attend the EOT visit 4 weeks after SUBLOCADE administration.
- 10. Any subject with ongoing AEs or concomitant medications at the EOT/ET Visit will also be followed up by telephone 4 weeks later for a safety follow up to assess the ongoing AEs or concomitant medications only.
- 11. A detailed detox and MOUD treatment history will be collected at screening. For those subjects who have enrolled in the study prior to approval of protocol amendment 1, their detox and MOUD treatment history will be collected retrospectively at their next visit.

2 STATISTICAL HYPOTHESES

For this single arm study, the analysis methods are descriptive. Therefore, statistical testing and hypotheses are not applicable.

2.1 Multiplicity Adjustment

There is no multiplicity adjustment.

3 SAMPLE SIZE DETERMINATION

Up to 25 adult subjects with moderate to severe OUD are planned to be enrolled into the study.

4 POPULATIONS FOR ANALYSIS

The safety population will consist of all subjects who received at least 1 dose of SUBLOCADE in this study and will be the primary population for all analyses. All subjects who were screened received SUBLOCADE. Therefore, a screened population was not defined as it would comprise the same set of subjects.

5 STATISTICAL ANALYSES

5.1 General Considerations

5.1.1 INDV-6000-403 Data

Per the Schedule of Assessments (**Table 3**), some data will not be re-collected in this study, as the INDV-6000-403 data will be used. Further details of the transfer of these data into the INDV-6000-404 database are described in the analysis sections below.

5.1.2 Statistical Analyses and Coding

Statistical analyses will be performed using version 9.4 (or higher) of SAS.

The AEs and medical/psychiatric conditions will be coded using the process and MedDRA version per the study coding guidelines.

The final analysis will occur after the database lock.

5.1.3 Treatment Label

The treatment label will be presented in the tables, listings and figures (TLFs) as SUBLOCADE.

5.1.4 Study Definitions

5.1.4.1 Subject Screening

Study screening begins once written informed consent is obtained; the same subject identification number from INDV-6000-403 will be assigned.

5.1.4.2 Enrolled

A subject will be considered enrolled if he/she receives at least 1 dose of SUBLOCADE in this study.

5.1.4.3 Not Enrolled

A subject will be considered not enrolled if written informed consent is obtained but the subject does not receive SUBLOCADE in this study. Reasons for not enrolling (e.g., withdrawal of consent, does/not meet specified inclusion or exclusion criteria) will be recorded in the case report form (CRF).

5.1.4.4 Treatment Period

Treatment period begins when the SUBLOCADE injection is given on Day 1 and ends after all assessments have been made at the EOT Visit.

5.1.4.5 Study Completion

A subject will be considered to have completed the study if they have completed the last injection visit (Injection 5) and the scheduled EOT visit.

5.1.4.6 Early Termination

A subject will be considered an Early Termination (discontinued) if he/she is dosed with SUBLOCADE and does not complete the study (did not complete the last injection visit [Injection 5]) and the scheduled EOT visit.

5.1.5 General Conventions for Analysis

Continuous variables will be summarised using the descriptive statistics mean, standard deviations (SD), median, minimum and maximum, unless other statistics are specified. Categorical variables will be reported as frequency counts (including number missing) and the percentage of subjects in corresponding categories.

Individual subject data will be presented by subject in data listings. Data listings will include all data collected from the initial screening visit to the Safety follow-up visit (including unscheduled visits).

The derivation of Study Day will be made relative to the date/time of the first administration of SUBLOCADE in this study.

Observed data is used for analysis, unless handling of missing data is described otherwise within the analysis description or in Section 6.5.

If there are ≤ 6 AEs reported, only a listing and no AE summary tables will be produced, except for the table of AE occurrences used for public disclosure. The table of AE occurrences for public disclosure will only be produced if there are ≥ 1 AEs reported.

5.2 Subject Dispositions

The number and percentage of subjects who were screened and were enrolled or not enrolled (See Sections 5.1.4.2 and 5.1.4.3), and the reasons for not enrolling (if applicable), will be summarized for the screened population. The number and percentage of enrolled subjects who completed the study, discontinued and the reasons for discontinuing will be summarized.

The number and percentage of subjects failing entry criteria will be summarized overall and by individual criterion for the screened population.

The number and percentage of subjects in each analysis set will be summarized.

5.3 Primary Endpoint Analysis

The analysis will be performed using the safety population. See Section 6.5 for methods to handle missing data.

5.3.1 Treatment Emergent Adverse Events – Definition of Endpoint

A TEAE is defined as an AE observed after starting, that is having a start date/time on or after the date/time of the first administration of SUBLOCADE in this study. Any AEs ongoing at the INDV-6000-403 EOT were to be recorded in this study; however, note that these are not TEAEs in this study per this definition.

If subject experiences an event both prior to starting administration of SUBLOCADE and ongoing during the treatment, the event will be considered a TEAE (of the treatment) only if it has worsened in severity (i.e., it is reported with the date of worsening as the new start date/time) after starting administration of SUBLOCADE in this study.

Adverse events will be coded using the MedDRA dictionary and grouped by primary system organ class. The Investigator determines the intensity of AEs and the relationship of AEs to study therapy.

5.3.2 Treatment Emergent Adverse Events – Main Analysis Approach

If > 6 AEs are reported, the summaries will be produced as described below. Otherwise, no summaries and only the AE listing will be produced.

The number and percentage of subjects reporting TEAEs at any time during the treatment period (Section 5.1.4.4) will be presented by MedDRA system organ class (SOC) and preferred term (PT), each in descending order of frequency (then alphabetically in case of ties).

All TEAEs collected during the treatment period will be presented by system organ class and preferred term, each in descending order of frequency, unless otherwise specified.

If more than one TEAE is coded to the same PT for the same subject, the subject will be counted only once for that PT using the most severe and most related occurrence for the summarizations by severity and by relationship to the study medication.

5.4 Analysis of Other Safety Endpoints

Other safety endpoints include study-medication-related TEAEs, serious TEAEs, study medication-related serious TEAEs, TEAEs leading to treatment discontinuation and concomitant medications (see Section Error! Reference source not found.).

The analyses will be performed using the safety population if > 6 AEs are reported. See Section 6.5 for methods to handle missing safety data (e.g., partial dates).

5.4.1 Study Medication-related Adverse Events, Serious Adverse Events and Adverse Events Leading to Study Medication Discontinuation

The number and percentage of subjects reporting study medication-related TEAE, serious TEAE, study medication-related serious TEAE and TEAE leading to study medication discontinuation will be summarised by system organ class and preferred term, as described above in Section 5.3.2.

5.4.2 Prior and Concomitant Medications

Any medications ongoing at the INDV-6000-403 EOT were to be recorded in this study. The prior and concomitant medications will be listed.

5.5 Analysis of Other Safety Variables

The analyses will be performed using the safety population. See Section 6.5 for methods to handle missing safety data (e.g., partial dates).

5.5.1 Adverse Events – Additional Analyses

If > 6 AEs are reported, the summaries described below will be produced. If there are ≥ 1 but ≤ 6 AEs reported, only the AE occurrences summary will be produced.

The TEAE summary table will present the number and percentage of subjects reporting a TEAE in the categories listed in **Table 4**.

Table 4 TEAE Summary Categories

Category
Subjects with Any TEAEs
With Study Medication-Related TEAEs
With Serious TEAEs (SAE)
With Study Medication-Related Serious TEAEs
With Severe TEAEs
With TEAE Leading to Death
With TEAE Leading to Study Medication Discontinuation
With TEAE Leading to Study Medication Interruption
With TEAE Leading to Study Medication Dose Decrease
With TEAE Leading to Study Medication Dose Increase
With Serious TEAE Leading to Study Medication Discontinuation
With Serious TEAE Leading to Study Medication Interruption
With Serious TEAE Leading to Study Medication Dose Decrease
With Serious TEAE Leading to Study Medication Dose Increase

The additional categories of TEAE listed above in Table 4 will be summarized in the same manner as TEAEs (Section 5.3.2) if > 6 AEs are reported. TEAEs will also be summarized by maximum intensity, system organ class and preferred term. The number of occurrences of TEAEs and study medication-related TEAEs will be summarized by PT. In addition, the number and percentage of fatal and fatal study medication-related treatment-emergent SAEs will be summarized separately by PT.

If more than one TEAE is coded to the same SOC/PT for the same subject, the subject will be counted only once for that SOC/PT using the most severe and most related occurrence for the summarizations by severity and by relationship to the study medication.

If > 6 AEs are reported, listings will be presented for subjects with AEs, SAEs, AEs leading to discontinuation, and subjects who died (if any). Otherwise, the only listing of AEs presented will be all the AEs listing.

AEs that are not treatment emergent (i.e., AEs that were ongoing at the time of completion of the feeder study INDV-6000-403 and recorded in this study database) will be listed.

5.5.2 Extent of Exposure

The number and percentage of subjects who received at least 1 dose of SUBLOCADE and who received 1, 2, 3, 4 or 5 doses of SUBLOCADE will be summarized. The number and percentage of subjects who received SUBLOCADE 300mg and 100mg will be summarized by injection. The data will be listed.

5.5.3 Adverse events of special interest (AESI)

Adverse events of special interest are:

- SUBLOCADE depot removal
- Occurrences of ALT $>3 \times$ ULN and bilirubin $>2 \times$ ULN (>35% direct)

The AESI will be included in the AE and SAE summaries and listings as reported.

5.5.4 Pregnancy Tests

The pregnancy test result data will be listed.

5.5.5 Drug Use History

The screening visit drug use history results will be transferred from the INDV-6000-403 database to serve as the screening visit results for this study.

The following information describes the transferred data:

- Dates of drug use history were collected as month and year.
- The overall lifetime drug use across all substances in years was derived by subject as (the latest Stop Date the earliest Start Date +1)/12.
- The lifetime use in years was derived for each drug class by subject, as the sum of the [(Stop Date Start Date +1) / 12] for each drug in the class used by the subject. Where use of individual drugs within a class overlapped, this overlapped time was not be double-counted in the derivation.
- For these derivations, missing end dates (month and year are missing) were set to the month and year of first study medication dose of transmucosal buprenorphine for

induction from the INDV-6000-403 study. Partial dates (i.e., only year is collected) will be imputed as follows:

- o Partial start dates were set to the first month of the year.
- o Partial end dates were set to the last month of the year.

The number and percentage of subjects reporting each drug class, the years of lifetime use overall and for each drug class, and the use in the last 30 days will be summarized using observed data.

An additional analysis will summarize the number and percentage of subjects who use any opioid via the I.V route.

The drug use history data will be listed.

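### Year-only drug-use stop dates go to December with no cap, so a recorded history can be extended past the first INDV-6000-403 dose

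*SAP*

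**What the plan says.** SAP section 5.5.5 (Drug Use History) takes the history from the 403 database and describes how durations were derived from dates held to the month. Footnote 2 to the schedule of assessments (Table 1 in the protocol, Table 3 in the SAP) and SAP section 6.6 confirm that the source is the 403 screening visit.

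Three imputation rules are given:

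- Stop date wholly missing: "missing end dates (month and year are missing) were set to the month and year of first study medication dose", meaning the transmucosal buprenorphine dose in 403.
- Start date with year only: "Partial start dates were set to the first month of the year".
- Stop date with year only: "Partial end dates were set to the last month of the year".

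Two durations are built from these dates. The overall figure is introduced with "The overall lifetime drug use across all substances in years was derived by subject as" and uses "the latest Stop Date the earliest Start Date +1)/12" (the minus sign is lost in the extracted text), which is a span from first to last use. The class figure adds up the periods for the drugs in a class, with the proviso "Where use of individual drugs within a class overlapped, this overlapped time was not be double-counted in the derivation". Both are then summarised in years.

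The section contains no check of an imputed stop date against the first 403 dose or the screening visit.

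**The concern.** The rule for a blank stop date recognises that the history cannot extend beyond the start of treatment in 403. The rule for a year-only stop date does not. When the stated year is the year of the first dose, December can lie after that dose, and so after the visit at which the subject was asked. The rule then credits the subject with months of use that nobody could have reported.

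It also produces a reversed ordering: a subject who supplied the year can be given a longer history than an otherwise identical subject who supplied nothing.

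The SAP applies a consistency check of this kind elsewhere. Section 6.5.1 pulls an imputed adverse-event start date back to the stop date if it would otherwise fall later. Section 5.5.5 has no counterpart.

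What is at stake is the accuracy of one descriptive baseline summary, which protocol section 14.4.3 and SAP section 5.5.5 both commit to report.

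**Working it through.** The documents report no lifetime-use result, so there is no figure to reproduce. The check applies the rules of section 5.5.5 to illustrative dates. The calendar dates are assumptions, because the documents give no subject-level data.

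**Inputs.** Year-only stop: December. Blank stop: month of the first 403 transmucosal dose, written m (1 to 12). Duration: (stop − start + 1)/12, in months converted to years. Maximum enrolment: 25 (SAP section 3).

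**Step 1, one subject.** Assume use began in January 2010 and the first 403 dose was in June 2019.

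- Stop recorded as 2019 only, so December 2019: 9 × 12 + (12 − 1) + 1 = 120 months = 10.0 years.
- Stop blank, so June 2019: 9 × 12 + (6 − 1) + 1 = 114 months = 9.5 years.

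The record with more information is 6 months longer, and all 6 months fall after the dose.

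**Step 2, general size.** For a year-only stop in the dosing year, the excess over the blank-date rule is 12 − m months.

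| Dose month | December rule (years) | Stop at dose month (years) | Excess (months) |
|---|---|---|---|
| January | 10.0 | 109/12 = 9.08 | 11 |
| June | 10.0 | 114/12 = 9.50 | 6 |
| December | 10.0 | 120/12 = 10.0 | 0 |

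The maximum is 11/12 = 0.92 years. If dose months were spread evenly over the year, the average would be (11 + 10 + … + 0)/12 = 66/12 = 5.5 months. Several affected records for one subject do not add up within a figure, because overlap is removed in the class figure and the overall figure uses only the latest stop.

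**Step 3, effect on a mean.** If k of n subjects are affected, the mean rises by at most (k/n) × 11/12 years. With n = 25:

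| k | Ceiling (11 months each) | At 5.5 months each |
|---|---|---|
| 1 | 0.037 years | 0.018 years |
| 5 | 0.183 years | 0.092 years |
| 25 | 0.917 years | 0.458 years |

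A class used by fewer subjects has a smaller n, so one record weighs more there, but the shift in a mean cannot exceed 0.92 years.

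**Step 4, where the rule does no such harm.** For a stop year before the dosing year, December may be later than the truth but is a possible date. The January rule for start dates also lengthens durations, by 0 to 11 months, but creates no impossible date. Both are ordinary conventions and are not part of this point.

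**The case against.** The strongest reply is that this is too small to matter. The study is descriptive with no hypotheses (SAP section 2), the primary endpoint is the proportion of subjects with treatment-emergent adverse events, and years of drug use is not an eligibility criterion, covariate, subgroup or population criterion. The fault needs a year-only stop in one particular calendar year, and there may be no such record. All of this stands. It limits the weight of the point but does not make the rule right.

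A second reply is that section 5.5.5 mostly describes, in the past tense, derivations already made in 403, so changing them here gives the same subjects different baseline values in the two studies. That is a real cost. The sentence introducing the partial-date rules uses the future tense, however, so it is not clear that these values are already fixed. A footnote deals with any difference.

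A reader might go further and infer that the overall figure is wrong because it counts drug-free years that the class figure leaves out. The documents do not support this. The span formula is openly stated and is a coherent description of time from first to last use. The class rule reads naturally as one start and one stop per drug, and a gap inside such a record is counted in both figures. The two separate only when gaps fall between recorded periods and no other recorded substance covers them. Whether the figures are set side by side as if comparable cannot be judged either, because the SAP introduction places table specifications in a separate document. What remains is a modest case for a clearer label.

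**Conclusion.** The point holds for the uncapped year-only stop date. Section 5.5.5 can place the end of use after the history was collected, and can give a longer duration than a blank date would. The excess is 0 to 11 months per affected record and at most about 0.04 years on a mean of 25 for each affected subject. No other section of either document corrects it.

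This rests on three things: that 403 screening preceded the first 403 transmucosal dose, as the word implies; that the rules were or will be applied as written; and that at least one year-only stop falls in the dosing year, which the documents neither show nor exclude.

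A reader might also infer that an inflated history misdescribes the population to which the safety result is extended. Neither document interprets or extends that result by years of drug use, so this does not follow. The point is a minor correction to a baseline summary and has no bearing on the primary endpoint.

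**What to change.** In SAP section 5.5.5, set a year-only stop date to the earlier of December of the stated year and the month of the first 403 transmucosal dose. This extends to partial dates the limit already used for blank ones. Add a footnote wherever the resulting values differ from those reported in 403. If the 403 derivation already applied such a cap, one sentence in section 5.5.5 saying so is enough.

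Optionally, label the overall figure *years from first to last use*, because it is a span across all substances while the class figure adds recorded periods with overlap removed.

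The cost is a few lines of programming on transferred data and the footnote; no new data are needed. The drawback is a possible small mismatch with the parent study's tables. If the outputs have already been produced, the SAP introduction provides for recording departures from the plan in the clinical study report, and the change can be documented there.
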